5.2 STUDY POPULATION

5.2.1 Approximate Number of Subjects

Approximately 100 Geisinger subjects who have TKA surgery at Geisinger will participate in this study (50 will be in the SOC group and 50 will be in the SOC+RelieVRx group).

5.2.2 Inclusion Criteria

For inclusion, the study subjects should fulfill the following criteria:

- 1. \geq 18 years old
- 2. Willing and able to read, comprehend, and sign the study informed consent form in English prior to study specific procedure
- 3. Scheduled for Total Knee Arthroplasty (TKA) surgery
- 4. Score of 1-3 based on the American Society of Anesthesiologists Physical Status Classification System
- 5. Attended the pre-op Total Joint Arthroplasty Patient Education class (Proven Recovery Program[©])
- 6. Agrees to be enrolled in Force Therapeutics, a web-based, digital rehabilitation and education program
- 7. Has family member, friend, or community support during post-surgical recovery period

5.2.3 Exclusion Criteria

For exclusion criteria, subjects should not enter the study if any of the following exclusion criteria are filled:

- 1. Diagnosed with chronic pain syndrome
- 2. Body Mass Index (BMI) ≥ 40
- 3. Current tobacco user at time of surgery
- 4. Uncontrolled sleep apnea
- 5. Bilateral TKA
- 6. Current or recent history (in past year) of substance abuse disorder

PI Name: [name] Research Protocol: July 25, 2019 Version 1.2 (03/17/20)

- 7. Uncontrolled diabetes (HbA1c \geq 7.0) 7.8 at time of surgery
- 8. History of Pulmonary Embolism (PE) or Deep Vein Thrombosis (DVT)
- 9. Currently being treated with blood thinners at time of surgery
- 10. Diagnosis of Rheumatoid Arthritis (RA)
- 11. Has Methicillin-resistant Staphylococcus aureus (MRSA)
- 12. Currently pregnant/breastfeeding or planning to in the next 3 months
- 13. Comorbidities including neurological, psychosocial, sensory, or other disorders that may impact pain perception
- 14. Diagnosis of epilepsy, dementia, migraines, or other neurological disorders that may prevent VR usage, and/or other medical conditions predisposed to nausea and dizziness
- 15. Hypersensitivity to flashing lights or motion
- 16. Claustrophobia
- 17. Lack of stereoscopic vision
- 18. Severe hearing impairment
- 19. Injury to eyes, face, or neck that prevents comfortable VR usage

5.3 RECRUITMENT

The primary and collaborating investigator(s) will identify potential subjects in their respective clinics that have elected to undergo primary TKA. These patients will also be pre-screened via manual chart review of their electronic health record (EHR) by the research team. Patients meeting the inclusion/exclusion criteria will be approached by an IRB approved study team member (e.g. primary and collaborating physicians, research project manager and/or project coordinator) during their orthopaedic clinic visit, orthopaedic health and physical, and/or Total Joint Class. Before asking for patient consent, the study will be explained in its entirety and the patient will have ample opportunity to ask any questions or express any reservations.

5.4 STUDY DURATION

5.4.1 Approximate Duration of Subject Participation

Subjects will participate in the study for approximately 4 months.

5.4.2 Approximate Duration of Study

This study will be completed in approximately two years. The end of the study is the last visit of the last subject or end of collection of data from the patient's electronic medical record (EMR).

PI Name: [name] Research Protocol: July 25, 2019 Version 1.2 (03/17/20)

5.5 **PROCEDURES**

Standard of Care: Both the SOC+RelieVRx group and the SOC group will be enrolled in the Geisinger ProvenRecovery Program[©], which includes a "My Rapid Recovery Kit" containing care instructions for mobility and nutrition, an antiseptic body wash to lessen the chances of infection, a spirometer to measure lung capacity, and immunonutrition drinks to avoid malnutrition and dehydration. Surgery through ProvenRecovery[©] is opioid avoiding and in many cases opioid free. During surgery, a patient's pain is controlled by targeting only the surgical area. Known as multi-modality pain management, this technique allows for effective pain control of just one area and eliminates additional pain sources. A combination of non-opioid medications is used, depending on the surgery, such as a local anesthesia, ibuprofen, acetaminophen, gabapentin, ketamine, and lidocaine.

Intervention: For all participants who are randomly assigned to the SOC+RelieVRx group, the RelieVRx headset will be provided by a study team member during the preoperative period, along with instructional materials. While in the hospital, use of the VR headset will be offered either in addition or as an alternative to SOC pain medication. The headset will be provided preoperatively, but patients will not be instructed to use the device until after their surgery. Patients will be instructed to use the device on the day of surgery after they are discharged from the Post Anesthesia Care Unit (PACU) to the inpatient unit, or at least 4 hours post-surgery. The device will then go with the patient upon discharge for use through the entire treatment period (i.e. 14 days). Participants will use the RelieVRx headset for 14 days postoperatively a maximum of 3 times per 24-hour period (morning, noon, and evening) for not more than 30 minutes consecutively. The patients will be instructed not to use the device while ambulating.

Assessments: In inpatient postoperative periods, pain will be assessed as per routine with a Numerical Pain Rating Scale (NPRS) of 0-10, where zero equals the lowest pain level and 10 equals the highest. This will be administered every 4 hours during the patient's hospital stay, and each time the patient requests pain medication, either intravenous or oral. After patients are discharged from the hospital, they will be asked to complete a paper or online REDCap diary to track their pain levels, opioid/non-opioid pharmacotherapy, and device use from home. The daily log will capture the NPRS at the same time each evening (± 2 hours). Participants will be asked to record their NPRS at least 2 hours after taking any pain medication. In the SOC+RelieVRx group, NPRS also will be recorded before (within 15 minutes prior to use) and immediately after each use of the RelieVRx device. Analgesic medication use will be recorded in terms of medication type, dose, and time of administration.

All participants will be enrolled in Force Therapeutics, a web-based, digital rehabilitation and education program. The patient is automatically enrolled when surgery is scheduled, and patient

PI Name: [name] Research Protocol: July 25, 2019 Version 1.2 (03/17/20)

participation is reinforced in the patient education class. This will allow for the easy collection of patient-reported outcome measures, such as VR-12 and KOOS Jr., after discharge. Outcomes data also may be collected via OBERD, a software system for patient-reported outcomes already in use at the study clinics. To assess opioid use, the investigators will query Pennsylvania's Prescription Drug Monitoring Program (PDMP) database. To maintain compliance with ABC-MAP Act 191 of 2014, study investigators will query the PDMP only for their existing patients.

The RelieVRx devices will collect information related to device usage (i.e. frequency and duration of use, experiences selected, etc.). Patients who are not using their RelieVRx device as prescribed and/or not completing the prescribed questionnaires in Force may be contacted via phone or email by the study team to further encourage participation. Participants will be asked to return their device to the study team at a routine postoperative clinic visit.

Outcome measures include:

- Pain will be assessed via the standard Geisinger Numerical Pain Rating Scale (NPRS) ranging 0-10 (0 = least amount of pain, 10 = worst amount of pain).
 - Every 4 hours during patient's hospital stay
 - Daily for the remainder of the first 14 postoperative days
 - Before (within 15 minutes prior to use) and immediately after each use of their device
- Physical function will be assessed by the KOOS Jr. (Knee Osteoarthritis Outcome)
- Analgesic medication use will be assessed in three ways:
 - Reviewing inpatient use as recorded in EMR
 - Extrapolating total milligrams of morphine equivalent doses filled from PDMP database through 90-days postoperative
 - Patient self-reported consumption
- Quality of life will be assessed using the Veterans RAND 12 Health Survey (VR-12) physical component score
- PACU length of stay (LOS)
- Hospital LOS
- Time to initial ambulation
- Clinic and emergency department visits within 90-days postoperative
- Inpatient readmissions for uncontrolled pain within 90-days postoperative
- Surgical complications, such as infection or delayed healing, within 90-days postoperative

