5.6 STUDY ENDPOINTS AND STATISTICAL PLAN

This study will evaluate two primary endpoints – effectiveness of a single use of RelieVRx in the reduction of acute postoperative pain by 20%; and overall effectiveness of RelieVRx as an opioid-sparing intervention, where opioid and non-opioid consumption is reduced by at least 20% over a 90-day postoperative period in the SOC+VR group compared to the SOC group.

Acute effectiveness will be evaluated using NPRS data collected before and after each use of RelieVRx (up to 3 times per day) over the 14-day postoperative period. NPRS is measured on a scale of 0-10, with 0 being the least amount of pain and 10 being the most. Because pain levels will vary by time of day administered and are expected to peak in the first 24-72 hours postoperatively and drop afterward, acute effectiveness will be evaluated at all stages of recovery. The expected 20% reduction after single use will be scaled relative to the pre-use pain score [e.g. users reporting a pre-VR pain level of 8 would need to report post-VR pain levels of 6.4 (8 * 80%) on average; users reporting pre-VR pain of 5 would need to report pain levels of 4 post-VR, etc.]. Each SOC+VR patient will use VR up to 44 times over the 14-day recovery period, requiring linear mixed model analysis to assess acute changes in pain scores while accounting for stage of recovery and other covariates, such as age, preoperative health status and opioid use, and postoperative complications. For interim and final endpoint analyses, pain %change scores will be calculated for each use and averaged for each patient across the 72-hour acute postoperative period, the following week, after 10 days, and overall. These averages will be evaluated using one-sample unpaired *t*-tests (or the nonparametric one-sample Wilcoxon signed-rank test, as needed for non-normal data).

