Overall effectiveness will be evaluated by tracking daily opioid usage 90 days postoperatively in both SOC and SOC+VR groups. Average MMEs (Morphine Milligram Equivalents) per day will be compared using unpaired Student's *t*-test (or the nonparametric Wilcoxon rank-sum test) in interim and final endpoint analyses. In addition, changes in usage over time will be evaluated using linear mixed models (or nonlinear models, given data shape), accounting for variations in recovery time across patients and other covariates, such as other analgesic medications used postoperatively, preoperative opioid use, and dosage changes. A sub-analysis will compare usage in the 14-day acute postoperative recovery period.

The secondary endpoint of this study is a comparison of the cumulative experience of pain over the 14-day acute postoperative period between SOC and SOC+VR groups. In order to quantify pain that fluctuates over time, NPRS pain scores will be plotted for each patient over the acute postoperative period, using straight-line interpolation between measurements. This approach will allow for incorporation of all data collected (even if some patients participate more than others), and will avoid overemphasis on a single outcome measure (e.g. pain on day 14). Percent-areaunder-the-curve (VAS-%AUC) measurement will be calculated for each patient by adding the

PI Name: [name] Research Protocol: July 25, 2019 Version 1.2 (03/17/20)

areas of consecutive trapezoids defined by time on the x-axis and pain level measurements on the y-axis (e.g. 100% would indicate pain scores of 10 across the entire time period; 50% would indicate a linear reduction from 10 to 0 over the same time period). In interim and final endpoint analyses, NPRS-%AUC accumulated to date will be compared between groups using an unpaired Student's *t*-test (or nonparametric equivalent). In addition, linear mixed models will be used to compare cumulative pain between SOC and SOC+VR groups over time, as well as pain experienced in the inpatient postsurgical period and following days.

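### Inpatient pain scores triggered by analgesic requests are not excluded from the between-arm pain analyses, although the intervention is meant to change how often patients make requests

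*Combined protocol and SAP*

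**What the plan says.** Section 5.5 (Assessments) sets the hospital rule: "This will be administered every 4 hours during the patient's hospital stay", "and each time the patient requests pain medication, either intravenous or oral". For the period after discharge it says "The daily log will capture the NPRS at the same time each evening (± 2 hours"), followed by "Participants will be asked to record their NPRS at least 2 hours after taking any pain medication". The second instruction sits with the diary text and is most naturally read as applying at home. In the RelieVRx arm only, "NPRS also will be recorded before (within 15 minutes prior to use) and immediately after each use of the RelieVRx device", with up to three uses a day.

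The outcome list later in Section 5.5 gives the 4-hourly score as the only routine inpatient pain measure and omits the request-triggered score. The events table (5.5.1) marks NPRS several times a day in hospital, which does not settle the matter.

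Section 5.6 builds one 14-day pain curve per patient by straight-line interpolation and presents the use of every collected measurement as an advantage. It also plans mixed models comparing cumulative pain between arms over time, "as well as pain experienced in the inpatient postsurgical period and following days". It neither restricts readings by type nor flags them. It does acknowledge, for the device-use endpoint, that "pain levels will vary by time of day administered".

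**The concern.** A 4-hourly score is taken whatever the patient feels. A request-triggered score is taken because the patient wants analgesia, so whether it exists depends on the outcome being measured. If such scores run higher than scheduled ones, an arm that asks less often contributes fewer high readings and looks less painful, even with identical pain.

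Request rates are expected to differ. Section 5.5 offers the headset in hospital as an addition to pain medication or in place of it, and reduced opioid use is a primary endpoint. The mixed models in 5.6 allow for data missing at random. That does not deal with extra readings generated by the pain itself.

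Direction matters too. Specific Aim 2 hypothesises comparable cumulative pain, and 5.6.1 mentions noninferiority requirements. An artefact that lowers recorded pain in the RelieVRx arm would favour that conclusion.

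A second question is the change of reading rule at discharge, from round-the-clock scores plus request scores to one evening diary score.

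**Working it through.** **The plan's own figure.** Section 5.6.1 gives %AUC 0.86 versus 0.79 with SD 0.1, so d = 0.07/0.1 = 0.7. A two-sample t-test (two-sided 5%, 80% power) needs 33.02, hence 34 per arm, or 68 in total. With 25% attrition, 34/0.75 = 45.3, hence 46 per arm, or 92. Both stated figures reproduce. The 0.86 and 0.79 are scaled to the starting score of 8.50: (8.50 + 6.16)/17 = 0.862 and (8.50 + 4.93)/17 = 0.790. On the 0–10 scale used below, the same difference is 0.733 − 0.672 = 0.061.

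**Assumed inputs.** The documents give no request rate, no extra pain at request and no expected stay. Ranges used: k = 0 to 4 requests per day, e = 1 to 3 NPRS points above a scheduled score, stay 24 to 72 hours. From the plan: 6 scheduled scores per day (24/4).

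**Inpatient mean of readings.** Request scores inflate a plain mean by e·k/(6 + k).

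| Change in requests per day | e = 1 | e = 2 | e = 3 |
|---|---|---|---|
| 4 to 2 | 0.40 − 0.25 = 0.15 | 0.80 − 0.50 = 0.30 | 1.20 − 0.75 = 0.45 |
| 4 to 3.2 (a 20% fall) | 0.40 − 0.35 = 0.05 | 0.80 − 0.70 = 0.10 | 1.20 − 1.04 = 0.16 |

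With scheduled scores only, the shift is 0 by design. A separate simulation with identical true pain in both arms gave 0.08 to 0.16 points when the chance of a request in a high-pain hour was halved, 0.25 to 0.33 when requests ceased, and −0.02 to 0.02 using 4-hourly scores only.

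**%AUC.** A simulation (1,500 patients per setting, same true course throughout, trapezoid rule as in 5.6) gave an inpatient %AUC of 0.595 at k = 4 and 0.567 at k = 2, for a 48-hour stay and e = 2. Time-weighted over 14 days this is 0.028 × 2/14 = 0.004. The largest value for halved requests is at 72 hours and e = 3: (0.600 − 0.568) × 3/14 = 0.007. Only if requests vanish in that same setting does it exceed 0.01: (0.600 − 0.518) × 3/14 = 0.018.

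**Offset by pre-session scores.** If sessions replace 2 of 4 daily requests and the pre-use score is taken at the same raised pain level, inpatient %AUC is 0.601 (no post-use drop) or 0.589 (20% drop), against 0.596 with 4 requests. The shift largely disappears.

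**Discharge.** Scheduled scores fall from 6 a day to 1. For stays of 1, 2 or 3 days, 6/19 = 32%, 12/24 = 50% or 18/29 = 62% of scheduled scores come from the hospital. With flat true pain of 5.0, k = 4 and e = 2, the inpatient mean is 5.8. The step at discharge is then −0.8 if evening scores are unbiased, −1.8 if they read 1 point low and +0.2 if they read 1 point high. If stay differs between arms by one day, and the two rules differ by 0.5 to 2 points, %AUC differs by 0.5/(14 × 10) = 0.004 to 2/(14 × 10) = 0.014.

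**The case against.** The strongest counter-argument is that the plan may never analyse request scores. The outcome list omits them, 5.7.1 points to that list as complete, and 5.5 describes inpatient scoring as routine care. This makes the plan ambiguous, but it does not override 5.6, which admits all collected readings. The choice would be left to the analyst after the data are in.

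Several further points stand.

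- A reader might infer that fewer requests must lower recorded inpatient pain. The documents do not support that. It requires request scores to be analysed and to run higher than scheduled scores, and pre-session scores may take their place. That offset is accidental, however, and itself depends on which readings are used.
- A reader might infer that the switch at discharge biases the trial, or forces recorded pain down. Both arms follow the same routine rule, and the sentence on inpatient and later pain reads most naturally as arm against arm within each period. The 2-hour instruction is a minimum gap with no maximum, so it does not establish a medicated reading. The step could go either way.
- The 20% target is for consumption. If requests fell in the same proportion, the shift at e = 2 would be 0.10 points, against an SD of 2.0 in 5.6.1.
- The 0–10 scale caps e. At the mean of 8.50 after surgery only 1.5 points remain, so e = 2 or 3 is possible on average only later (10 − 6.16 = 3.84 on day 2).
- A plain mean of readings is not the planned summary. It is the closer guide for mixed models that take each reading as a row.

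**Conclusion.** The concern holds in a limited form. As written, Section 5.6 admits outcome-dependent readings whose frequency the intervention is meant to change, and Section 5.5 is inconsistent on whether they are outcome data. The exposure is the inpatient between-arm comparison and any reading-level pain model. There the shift is about 0.1 to 0.45 NPRS points with no true difference, and less in the mildest setting. It favours the comparable-pain hypothesis. The size rests entirely on assumed request rates and assumed extra pain at request, and pre-session scores could cancel it if they are also analysed.

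It would be tempting to say that the 14-day secondary endpoint is compromised. It is not: the movement is about 0.01 or less for halved requests, against a planned 0.07. The discharge change affects the arm comparison only if length of stay or request rates differ by arm. Its main consequence is that a within-arm change from hospital to home cannot be read as recovery, since the artefact's size and sign are unknown.

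**What to change.** 1. Reconcile the Assessments text and the outcome list in 5.5 on whether request-triggered scores are outcome data.
2. State in 5.6 that the between-arm %AUC and the pain mixed models use only scheduled scores common to both arms: 4-hourly in hospital, evening diary at home. Flag each score as scheduled, request-triggered or device-related. Keep request-triggered scores for description or for an all-readings sensitivity analysis.
3. Add a sensitivity analysis on one evening score per day for all 14 days, using the inpatient 4-hourly score nearest the diary time and then the diary score. This is only approximately like-for-like, because the inpatient score does not carry the 2-hour instruction. Recorded administration times can be used to select or flag it.
4. Do not interpret the inpatient-to-home change as recovery without that analysis.

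The cost is SAP wording, a reading-type flag and one or two sensitivity analyses. No visits are added, and the 68 evaluable and 92 enrolled patients are unchanged. The downside is that some inpatient readings are left out of the main pain comparison.

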4 SPECIFIC AIMS

4.1 SPECIFIC AIM 1

Among standard of care (SOC) plus RelieVRx (SOC+RelieVRx) group, compare pain scores before and after use of RelieVRx. *Hypothesis: Acute postoperative pain scores will decrease by at least 20% or 2 points on a 0-10 Numerical Pain Rating Scale (NPRS) after each use of RelieVRx*.

4.2 SPECIFIC AIM 2

Compare pain scores between the SOC group and SOC+RelieVRx group. *Hypothesis: Cumulative pain scores will be comparable among the SOC+RelieVRx group and SOC group.*

4.3 SPECIFIC AIM 3

Compare opioid use between the SOC group and SOC+RelieVRx group. *Hypothesis: Opioid consumption will be reduced by at least 20% over a 90-day postoperative period in the SOC+RelieVRx group compared to the SOC group.*

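### The evening diary pain score is spaced from pain medication but not from a RelieVRx session, so the 14-day %AUC can be biased between arms if relief after a session is short

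*Combined protocol and SAP*

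**What the plan says.** Section 5.5 (Procedures, Assessments) gives both arms one home pain score a day after discharge: "The daily log will capture the NPRS at the same time each evening (± 2 hours"). On medication it adds: "Participants will be asked to record their NPRS at least 2 hours after taking any pain medication".

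The Intervention paragraph of the same section allows the headset "a maximum of 3 times per 24-hour period (morning, noon, and evening) for not more than 30 minutes consecutively", for 14 days. In the test arm only, "NPRS also will be recorded before (within 15 minutes prior to use) and immediately after each use of the RelieVRx device". No section sets an interval between a session and the evening diary score.

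Section 5.6 builds the secondary endpoint for each patient by trapezoids over 14 days, "using straight-line interpolation between measurements", and says: "This approach will allow for incorporation of all data collected (even if some patients participate more than others"). It does not say whether the scores taken around sessions enter this curve. Aim 1 in Section 4 expects a dip: "Acute postoperative pain scores will decrease by at least 20% or 2 points on a 0-10 Numerical Pain Rating Scale (NPRS) after each use". Aim 2 expects cumulative pain to be comparable between arms.

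**The concern.** The diary rule treats two sources of short-term relief differently. Medication, which both arms use, is separated from the score by at least 2 hours. The device, which one arm uses, is not. A test-arm patient who finishes an evening session and then fills in the diary has followed the protocol, yet has scored pain at the point where the sponsor expects it to be lowest.

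With one shared score a day, each score carries half of the 24 hours before it and half of the 24 hours after it. A dip lasting an hour or two can then be counted as a full day of lower pain. What is at stake is the reading of Aim 2. If test-arm patients took less opioid and had somewhat more pain through the day, a low evening score could hide it and the arms would look comparable.

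**Working it through.** **The plan's own figure (Section 5.6.1).** The difference is 0.07 with SD 0.1, so d = 0.7. A two-sided two-sample t-test at 5% with 80% power needs 33.02 per group, rounded up to 34, or 68 in total. With 25% attrition, 34/0.75 = 45.3, rounded up to 46 per group, or 92. Both stated figures reproduce. Nothing below changes them, because the point concerns when pain is measured.

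**Inputs from the documents.** Pain is 8.50 after the procedure and 6.16 on day 2, and the AUC SD is 0.1, or 10 points (Section 5.6.1). The drop per session is 20% and the maximum is three sessions a day (Sections 4 and 5.5).

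**Assumptions.** Pain falls linearly from 6.16 on day 2 to 3 on day 14 (range 2 to 4.93). Discharge is on day 2. All three sessions are used, and there is no benefit between dips. Let *f* be the share of evening scores that fall in a dip and *h* the hours of relief per session. The documents give neither.

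**Area under the pain curve**, as a percentage of 10 × 14 = 140 score-days (the scale defined in Section 5.6):
- Days 0–2: (8.50 + 6.16)/2 × 2 = 14.66
- Days 2–14: (6.16 + 3)/2 × 12 = 54.96
- Total: 69.62/140 = 49.7 points, of which days 2–14 are A = 54.96/140 = 39.3 points

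**Formulas**, using evening scores only after discharge:
- Recorded fall = 0.20 × f × A
- True fall = 0.20 × A × 3h/24
- Net bias = 0.20 × A × (f − h/8)

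| f | Recorded fall | True fall, h = 1 to 2 | Net bias |
|---|---|---|---|
| 25% | 2.0 | 1.0 to 2.0 | 0 to 1.0 |
| 50% | 3.9 | 1.0 to 2.0 | 2.0 to 2.9 |
| 100% | 7.9 | 1.0 to 2.0 | 5.9 to 6.9 |

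With day-14 pain of 2 or 4.93, A is 35.0 or 47.5, and the recorded fall at f = 50% is 3.5 or 4.8.

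**Where the bias is zero.** It vanishes when f = h/8. At h = 4 the true fall is 39.3 × 0.20 × 12/24 = 3.9 points, equal to the recorded fall at f = 50%. A lower share would then understate the device's benefit.

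**Chance of p < 0.05 from the net bias alone** (f = 50%, d about 0.20 to 0.29): roughly 12% to 22% at 34 per group and 16% to 31% at 50 per group, against a nominal 5%.

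**Dependence on scale.** The plan's 0.86 and 0.79 reproduce if the AUC is scaled to 8.50: (8.50 + 6.16)/17 = 0.862 and (8.50 + 4.93)/17 = 0.790. On that scale, with pain falling from 8.50 to 6.16 over 14 days and discharge after 1 to 3 days, the recorded fall at f = 50% is 0.066 to 0.080. That is 94% to 114% of the planned 0.07, before any true effect is subtracted.

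**If the session scores also enter the curve.** Take the same 8.50-to-6.16 course and scaling, with sessions assumed at 8:00, 12:30 and 20:00 and pain back to its course between sessions. The recorded test-arm AUC then falls by:
- 0.077 with the diary score right after the evening session
- 0.075 with it just before, because the last post-session score is interpolated overnight
- 0.048 with it 2 hours after

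A diary rule alone therefore does little under this reading.

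**The case against.** The strongest reply is that the direction of the bias rests on two unknowns. If relief lasts about 4 hours, the 50% case is unbiased and lower shares work against the device. That stands. A reader might infer that the bias always favours RelieVRx, but the documents do not establish it.

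A reader might also take the whole 3.9-point shift as bias. Tested as such, it would give p < 0.05 in 36% of trials at 34 per group and 49% at 50. Part of the shift is real benefit, so only the net figures should be used.

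Three further readings go beyond the text:
- Evening is a named time under a maximum of three uses, and the diary hour is not given. An evening session inside the diary window is possible, not scheduled.
- Section 5.5 gives no reason for the 2-hour medication rule. That it is meant to avoid short-term drug relief is an inference; what the text shows is only that the device has no matching rule.
- The evening score may not be the only shared home score. The table in Section 5.5.1 lists NPRS under a home column headed as several times a day, although Section 5.5 describes one daily score. More shared scores would reduce the weight of each.

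It is also fair to say that Section 5.6 interpolates between all measurements, not from evening to evening. The bias figures above therefore hold only for an AUC limited to evening scores after discharge. The wider reading brings the session scores in by a second route; it does not remove the asymmetry. Finally, the SD of 0.1 belongs to the scale that gives 0.86 and 0.79, so applying it to a curve averaging 49.7% is an assumption.

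**Conclusion.** The gap is real, and no other section closes it: the evening score has a rule for medication and none for the device under test. Whether it biases the %AUC depends on how long relief lasts and how often the diary follows a session. With 1 to 2 hours of relief, a 20% dip and half of the scores after a session, the net bias is about 2.0 to 2.9 points against a planned 7. At a quarter of scores it is 0 to 1.0. At about 4 hours of relief it is nil in the 50% case and reverses at lower shares.

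These figures rest on the assumed pain course, discharge day and use of all three sessions. The documents do not support a claim that the endpoint is biased in favour of RelieVRx, only that it can be. The documents also give no basis for estimating how much worse pain might be hidden. The endpoint is secondary and the remedy is small, so this is a worthwhile, inexpensive improvement and not a flaw in the trial's main design.

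**What to change.** 1. In Section 5.5, state that the test-arm evening diary NPRS is recorded before the evening session or at least 2 hours after the end of the last session. The medication rule stays as it is.
2. Have the diary record the clock time of each score and each session. A reader might assume the device logs already supply session times, but Sections 5.5 and 5.7.1 name only items such as frequency and duration of use, and Section 5.7.1 has the data aggregated before transfer.
3. In Section 5.6, build the between-arm %AUC from the time points common to both arms, and keep the scores before and after sessions for Aim 1. Without this, step 1 has limited effect.
4. Repeat the %AUC comparison without evening scores entered within 2 hours after a session.

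The cost is one diary instruction, added time fields, one sentence on the AUC and one sensitivity analysis. Sample size and use of the device are unchanged. The downside is that real relief in the 2 hours after an evening session is not counted. Scores already collected at unrecorded times cannot be re-timed, so the rule has to be in place before collection.
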